## **14.6.** Inspection of Records

According to the ICH guidelines for GCP, the Sponsor or designee must verify data entered in the eCRF entries against the source documents. The objective of source document verification is to comply with GCP and international regulatory requirements and to reduce the risks of fraud. Source document verification means ensuring that source documents are an accurate and confirmable reflection of the patient's evaluations during participation in the study and that all relevant information recorded in the source document is accurately entered into the eCRF. All source documents should be correctly labeled and filed and associated with a single, verifiable patient.

All data required for this study should be captured in source notes. No data obtained by the Investigator or other study personnel should be captured directly in the eCRF. All source documents pertaining to this study will be maintained by the Investigator and made available for

inspection by authorized persons. If electronic progress notes and other electronic source documents are not compliant with applicable regulatory guidance, they are not considered a valid source for this study. All patient progress notes must be dated and signed at the time of the visit. The Sponsor reserves the right to terminate the study for refusal of the Investigator to supply original source documentation for this clinical study.

The Investigator will note in a source independent from the eCRF the following information:

- Information to confirm that the patient exists [e.g., initials, date of birth (applicable per local regulations), and sex];
- Confirmation that the patient satisfies the inclusion/exclusion criteria;
- Confirmation that the patient is taking part in the clinical study;
- Confirmation of the informed consent process;
- Visit dates and documentation of protocol assessments and procedures;
- Information concerning all adverse events;
- Details of concomitant and investigational medications.

Source document verification is not a substitute for clinical study monitoring, the purpose of which is to ensure that the protocol has been followed correctly, the eCRF has been fully and accurately completed, source document verification has been carried out, and the study timelines and enrollment goals and requirements have been met. In light of the COVID-19 pandemic, source document verification may occur remotely. Additional detail on remote source document verification will be provided in the study plans.

#### 14.7. Retention of Records

Clinical Investigators must retain study records from investigational drug studies for a period of 2 years following the date a marketing application is approved for the drug for the indication for which it is being investigated; or, if no application is to be filed or if the application is not approved for such indication, until two years after the investigation is discontinued and the appropriate regulatory authority is notified.

The Investigator must maintain all study documentation as confidential, and take measures to prevent accidental or premature destruction of these documents.

The Investigator must notify the Sponsor prior to destroying any study essential documents.

If the Investigator can no longer ensure archiving, he/she shall inform the Sponsor. The relevant records shall be transferred to a mutually agreed upon designee.

### 15. PUBLICATION POLICY

The results of this study may be published in a medical publication, journal, or another public dissemination, or may be presented at a medical conference or used for teaching purposes. Additionally, this study and its results may be submitted for inclusion in all appropriate health authority study registries, as well as publication on health authority study registry websites, as required by local health authority regulations. Selection of first authorship will be based on several considerations, including, but not limited to study participation, contribution to the protocol development, and analysis and input into the manuscript, related abstracts, and presentations in a study.

## 17. APPENDICES

17.1. Clinical Laboratory Assessments

| Hematology                          | Chemistry                   | Pregnancy Testing             |
|-------------------------------------|-----------------------------|--------------------------------------|
| Complete blood count                | Alanine aminotransaminase   | Human chorionic gonadotropin         |
| Absolute neutrophil count           | Albumin                     | (females of childbearing potential   |
| Absolute eosinophil count           | Alkaline phosphatase        | only) serum (screening) and urine    |
| Platelet count                      | Amylase                     | (Treatment Period and Safety Follow- |
| White blood cell count with         | Aspartate aminotransaminase | up Visit, if applicable)             |
| differential                        | Total bilirubin             |                                      |
| Absolute reticulocyte count         | Direct bilirubin            |                                      |
| Hemoglobin A1c                      | Indirect bilirubin          |                                      |
|                                     | Blood urea nitrogen         |                                      |
|                                     | C-Reactive Protein (CRP)    |                                      |
|                                     | Calcium                     |                                      |
|                                     | Carbon dioxide              |                                      |
|                                     | Chloride                    |                                      |
|                                     | Creatinine                  |                                      |
|                                     | Creatine kinase             |                                      |
|                                     | Glucose                     |                                      |
|                                     | Lipase                      |                                      |
|                                     | Total protein               |                                      |
|                                     | Phosphorus                  |                                      |
|                                     | Potassium                   |                                      |
|                                     | Sodium                      |                                      |
|                                     | Uric Acid                   |                                      |
| Serology                            | Lipids                      | Other                                |
| Hepatitis B Surface Antigen (HBsAg) | Total cholesterol           | Tuberculosis                         |
| Hepatitis C Virus Antibodies (HCV   | Low-density lipoprotein     | Thyroid stimulating hormone          |
| Ab)                                 | High-density lipoprotein    |                                      |
|                                     | Triglycerides               |                                      |

# 17.2. Severity of Alopecia Tool (SALT)

Olsen/Canfield

| Quadrant | Raw Score
(% hair loss) |  |
|----------|----------------------------|--|
| Left     | % loss                     |  |
| Right    | % loss                     |  |
| Тор      | % loss                     |  |
| Back     | % loss                     |  |

| Quadrant | Quadrant
Surface
Area | Calculated Score (Raw Score x Surface Area %) |
|----------|-----------------------------|---|
| Left     | 18%                         | ( % loss) x (0.18) =                          |
| Right    | 18%                         | ( % loss) x (0.18) =                          |
| Тор      | 40%                         | ( % loss) x (0.40) =                          |
| Back     | 24%                         | ( % loss) x (0.24) =                          |

| Total SALT Score (Sum of Calculated Scores for the 4 quadrants) |  |
|--|--|
|  |  |

## 17.3. Global Impression Scales

## 17.3.1. Clinical Global Impression of Severity (CGI-S)

How would you rate the severity of the patient's alopecia areata at this time:

- 1. Normal, no hair loss
- 2. Borderline hair loss
- 3. Mild hair loss
- 4. Moderate hair loss
- 5. Marked hair loss
- 6. Severe hair loss
- 7. Among the most extreme hair loss

## 17.3.2. Clinical Global Impression of Improvement (CGI-I)

Compared to the patient's alopecia areata prior to treatment at Baseline, the patient's current state of alopecia areata is:

- 1. Very Much Improved
- 2. Much Improved
- 3. Minimally Improved
- 4. No Change
- 5. Minimally Worse
- 6. Much Worse
- 7. Very Much Worse

### 17.3.3. Patient Global Impression of Severity (PGI-S)

How would you rate the severity of your alopecia areata at this time:

- 1. Normal, no hair loss
- 2. Borderline hair loss
- 3. Mild hair loss
- 4. Moderate hair loss
- 5. Marked hair loss
- 6. Severe hair loss
- 7. Among the most extreme hair loss

### 17.3.4. Patient Global Impression of Improvement (PGI-I)

Compared to my alopecia areata prior to treatment at Baseline, my current state of alopecia areata is:

- 1. Very Much Improved
- 2. Much Improved
- 3. Minimally Improved
- 4. No Change
- 5. Minimally Worse
- 6. Much Worse
- 7. Very Much Worse

## 17.4. Patient Reported Outcome

## 17.4.1. Satisfaction of Hair Patient Reported Outcome (SPRO)

| How satisfied are you with the hair on your scalp today | ? |
|---|---|
| ₅ Very dissatisfied                                     |   |
| 4 Dissatisfied  |   |
| 3 Neither satisfied nor dissatisfied                    |   |
| 2 Satisfied   |   |
| ı Very satisfied  |   |

## 17.4.2. Quality of Hair Patient Reported Outcome (QPRO)

For the next set of questions, please choose the best answer that represents how you feel today.

| 1. | How satisfied are you with the thickness of the hair on your scalp?       | √S□
Very
dissatisfied | 4
Dissatisfied  | 3 Neither satisfied nor dissatisfied     | 2
Satisfied | ı□
Very
satisfied |
|----|---|-----------------------------|--------------------|--|----------------|-------------------------|
| 2. | How satisfied are you with the evenness of the hair on your scalp? | √S
Very
dissatisfied  | 4
Dissatisfied  | Neither
satisfied nor
dissatisfied | 2 Satisfied    | ı□
Very
satisfied |
| 3. | How satisfied are you with your eyebrows?                                 | yery
dissatisfied        | 4_
Dissatisfied | Neither
satisfied nor
dissatisfied | 2 Satisfied    | ı Very
satisfied     |
| 4. | How satisfied are you with your eyelashes?                                | 5
Very
dissatisfied   | 4
Dissatisfied  | Neither
satisfied nor
dissatisfied | 2
Satisfied | ı□
Very
satisfied |

# 17.5. Hospital Anxiety and Depression Scale (HADS)

#### Hospital Anxiety and Depression Scale (HADS)

Tick the box beside the reply that is closest to how you have been feeling in the past week.

Don't take too long over you replies: your immediate is best.

| D | Α   |  | D | Α |   |
|---|-----|--|---|---|---|
|   |     | I feel tense or 'wound up':  |   |   | I feel as if I am slowed down:  |
|   | 3   | Most of the time   | 3 |   | Nearly all the time   |
|   | 2   | A lot of the time  | 2 |   | Very often  |
|   | 1   | From time to time, occasionally  | 1 |   | Sometimes   |
|   | 0   | Not at all   | 0 | - | Not at all  |
|   | 0   | 140t at all  | 0 |   | Not at all  |
|   |     | I still enjoy the things I used to enjoy:                                    |   |   | I get a sort of frightened feeling like 'butterflies' in the stomach: |
| 0 |     | Definitely as much   |   | 0 | Not at all  |
| 1 |     | Not quite so much  |   | 1 | Occasionally  |
| 2 |     | Only a little  |   | 2 | Quite Often   |
| 3 |     | Hardly at all  |   | 3 | Very Often  |
|   |     | 1  |   |   |   |
|   |     | I get a sort of frightened feeling as if something awful is about to happen: |   |   | I have lost interest in my appearance:                                |
|   | 3   | Very definitely and quite badly  | 3 |   | Definitely  |
|   | 2   | Yes, but not too badly   | 2 |   | I don't take as much care as I should                                 |
|   | 1   | A little, but it doesn't worry me  | 1 |   | I may not take quite as much care                                     |
|   | 0   | Not at all   | 0 |   | I take just as much care as ever                                      |
|   |     | I can laugh and see the funny side of things:                                |   |   | I feel restless as I have to be on the move:                          |
| 0 |     | As much as I always could  |   | 3 | Very much indeed  |
| 1 |     | Not quite so much now  |   | 2 | Quite a lot   |
| 2 |     | Definitely not so much now   |   | 1 | Not very much   |
| 3 |     | Not at all   |   | 0 | Not at all  |
|   |     | Worrying thoughts go through my mind:  |   |   | I look forward with enjoyment to things:                              |
|   | 3   | A great deal of the time   | 0 |   | As much as I ever did   |
|   | 2   | A lot of the time  | 1 |   | Rather less than I used to  |
|   | 1   | From time to time, but not too often   | 2 |   | Definitely less than I used to  |
|   | 0   | Only occasionally  | 3 |   | Hardly at all   |
|   |     | I feel cheerful:   |   |   | I get sudden feelings of panic:                                       |
| 3 |     | Not at all   | - | 3 | Very often indeed   |
| 2 |     | Not often  | - | 2 | Quite often   |
| 1 |     | Sometimes  | - | 1 | Not very often  |
|   | - 0 |  |   | - |   |
| 0 |     | Most of the time   | , | 0 | Not at all  |
|   |     | I can sit at ease and feel relaxed:  |   |   | I can enjoy a good book or radio or Typrogram:                        |
|   | 0   | Definitely   | 0 |   | Often   |
|   | 1   | Usually  | 1 |   | Sometimes   |
|   | 2   | Not Often  | 2 |   | Not often   |
|   | 3   | Not at all   | 3 |   | Very seldom   |

Please check you have answered all the questions

| Scorin | g:                                      |             |
|--------|---|-------------|
| Total  | score: Depression (D)                   | Anxiety (A) |
| 0-7    | = Normal                                |             |
| 8-10   | = Borderline abnormal (borderline case) | )           |
| 11-21  | = Abnormal (case)                       |             |

# **VERSION HISTORY**

SAP Version	Version Date	Change(s)	Rationale
1.0	2022-06-29	First version	

# 1. LIST OF ABBREVIATIONS

Abbreviation	Term
ANCOVA	Analysis of Covariance
ATC	Anatomical-Therapeutic-Chemical
BELA	Brigham Eyelash Tool for Alopecia
BETA	Brigham Eyebrow Tool for Alopecia
BID	Twice daily dosing
CGI-I	Clinician Global Impression of Improvement
CGI-S	Clinician Global Impression of Severity
CI	Confidence interval
CSR	Clinical study report
CTCAE	Common terminology criteria for adverse events
DMC	Data Monitoring Committee
ECG	Electrocardiogram
eCRF	Electronic case report form
FCS	Fully conditional specification
FDA	Food and Drug Administration
HADS	Hospital Anxiety and Depression Scale
IQR	Interquartile range
LS	Least squares
MAR	Missing at random
MedDRA	Medical Dictionary for Regulatory Activities
MI	Multiple imputation
MMRM	Mixed effect model of repeated measures
MNAR	Missing not at random
PCS	Potentially clinically significant
PGI-I	Patient Global Impression of Improvement
PGI-S	Patient Global Impression of Severity
QPRO	Quality of Hair Patient Reported Outcome
SALT	Severity of Alopecia Tool
SAP	Statistical analysis plan
SPRO	Satisfaction of Hair Patient Reported Outcome

TEAE	Treatment-emergent adverse events
WHO	World Health Organization

### 2. PURPOSE OF THE ANALYSES

This statistical analysis plan (SAP) provides a detailed description of the strategy and statistical methodology to be used for analysis of data from the North American CP543.3002 protocol dated 23FEB2021 and the European Union CP543.3002 protocol dated 12MAR2021. The statistical analyses outlined within both versions of the protocol are aligned.

The purpose of the SAP is to describe the pre-specified statistical approaches to the analysis of study data prior to database lock. This analysis plan is meant to supplement the study protocol. If differences occur between analyses described in the SAP and the current protocol, those found in this SAP will assume primacy. Any deviations from this plan will be described in the Clinical Study Report (CSR).

#### **3. PROTOCOL SUMMARY**

This is a double-blind, randomized, placebo-controlled multicenter study to evaluate the efficacy and safety of CTP-543 in adult patients with moderate to severe alopecia areata. Patients will be between 18 and 65 years of age and experiencing an episode of hair loss associated with alopecia areata lasting at least 6 months and not exceeding 10 years. Patients not currently being treated for alopecia areata or with other treatments that might affect hair regrowth or immune response must have at least 50% hair loss as measured by Severity of Alopecia Tool (SALT) at Screening and Baseline.

An independent Data Monitoring Committee (DMC) will perform regular safety assessments based on a review of cumulative safety data. The DMC may advise study and/or treatment arm cessation due to intolerability at any time.

The Screening Period may last up to 28 days prior to initiation of study drug. The Treatment Period is a 24-week, double-blind, placebo-controlled period. Following the 24-week Treatment Period, patients will have the opportunity to continue receiving treatment in an Open-Label Extension study. If a patient does not wish to continue into the Open-Label Extension study, they will complete treatment at Week 24 and return in 4 weeks for the Post-Treatment Safety Follow-up to assess safety following treatment completion. The study design diagram can be found in Appendix 15.1.

Patients will provide appropriately-obtained informed consent prior to initiating any screening procedures. Patients meeting initial screening criteria will be eligible to continue to the Day 1 visit for review of eligibility and baseline assessments, including SALT assessment, physical examination, clinical laboratory assessments, and vital signs. Patients meeting all inclusion criteria and none of the exclusion criteria will be randomized to twice-daily treatment with either 12 mg CTP-543, 8 mg CTP-543 or placebo. Patients will be randomized in a 1:2:1 ratio (12 mg BID:8 mg BID:placebo). Randomization will be stratified by scalp hair loss into one of the following two categories: 1) Partial scalp hair loss (SALT  $\geq$  50 and < 95); 2) complete or near-complete scalp hair loss (SALT  $\geq$  95).

Patients will take the first dose of study drug in the clinic on Day 1 and will be instructed to take study drug daily approximately every 12 hours for the duration of the Treatment Period. Patients should dose study drug in the clinic on all Study Visit Days after clinical laboratory blood draws are completed. Other baseline assessments will include patient and clinician global impression of disease severity (PGI-S and CGI-S), Patient Reported Outcome for Satisfaction (SPRO) and Hair Quality (QPRO), the Hospital Anxiety and Depression Scale (HADS), and assessments for eyelash and eyebrow involvement. The schedule of assessments can be found in Appendix 15.2.

The double-blind, placebo-controlled Treatment Period will last 24 weeks. Assessment of treatment response using SALT for efficacy will occur at 4, 8, 12, 16, 20 and 24 weeks.

Patient safety will be monitored throughout the trial by the Investigator and supported by regular review by the Medical Monitor and DMC. Chemistry and hematology laboratory values will be assessed under fasted conditions bi-weekly for the first month of the treatment period, followed by every 4 weeks through the remainder of the study. Lipid levels will be assessed every 4 weeks throughout the Treatment Period. In light of the COVID-19 pandemic, challenges in the

conduct of study visits may arise from quarantines, site closures, and/or travel limitations. To ensure the safety of trial participants and to minimize risk to trial integrity, alternative methods for drug dispensation and assessments, including telemedicine visits and clinical laboratory blood draws at a local laboratory or via a Home Health Care agency, may be offered for those trial participants who may no longer have access to the investigational site. Significant cytopenias or other hematologic abnormalities will be managed by severity through dose interruption or discontinuation, and signs and symptoms of infection will be closely monitored and treated promptly. Patients who experience intolerable symptoms during treatment may discontinue treatment at the judgement of the Investigator, but will be followed for safety and efficacy assessments until Week 24, unless they withdraw consent. Patients may withdraw consent at any time.

Following the 24-week Treatment Period, patients will have the opportunity to continue receiving treatment in an Open-Label Extension study. If a patient does not wish to continue into the Open-label Extension study, they will complete treatment at Week 24 and return in 4 weeks for the Post-Treatment Safety Follow-up to assess safety following treatment completion.

#### 4. GENERAL ANALYSIS AND REPORTING CONVENTIONS

The following is a list of general analysis and reporting conventions to be applied to this study, unless otherwise specified. Departures from these general policies will be described, if applicable, in the appropriate sections of this SAP. When this situation occurs, the rules set forth in the specific section take precedence over the general policies.

All data displays (tables, listings, and figures) will have a header showing the sponsor company name, protocol number, page number, and display status (i.e. "DRAFT" or "FINAL"), as well as a footer indicating file name and run date/time. Summary tables and data listings will be summarized by active treatment versus placebo-treated patients (i.e., by treatment group) for efficacy and exposure, and by treatment group and overall otherwise. All data for analysis will be listed by-patient.

Categorical variables will be summarized using counts (n) and percentages (%) and will be presented in the form "n (xx.x)." If a count is 0, no percentage will be shown. If a percentage is 100%, 100 will be shown. To ensure completeness, summaries for categorical variables will include all categories, even if no patients had a response in a particular category. Unless otherwise specified, the denominator for each percentage will be based on the number of patients in the population being summarized (header n). Percentages will be rounded to one decimal place.

Continuous variables will be summarized using mean, standard deviation, minimum, maximum, median, and number of patients. The minimum and maximum will be the same precision as the original collected data. The mean and median will be reported to an additional level of precision than the original observations, and the standard deviation will be reported to two additional levels of precision than the original observations. The precision for some original collected data and derived variables are longer than required for clinical interpretation (eg, >15 decimals). In these situations, the number of decimal places will be determined by the table of precision included as an attachment.

Results of statistical models (ie, least-squares means, confidence intervals, risk differences) will be rounded to one additional decimal place from the original data, or a maximum of two decimal places. Standard error will be reported to an additional level of precision. Results which cannot be determined will be displayed as "NA", "NE", or similar.

For tests of hypothesis of treatment group differences, the associated p-value will be reported. All p-values will be rounded to four decimal places after assignment of statistical significance; pvalues that round to 0.0000 or are reported by SAS as zero will be presented as "≤0.0001"; pvalues that round to 1 or are reported by SAS as 1 will be presented as ">0.9999". P-values which are significant at a 0.05, 0.025, 0.01, 0.001, or 0.0001 level will be marked with asterisks. P-values which cannot be determined will be displayed as "NA". P-values are descriptive for outcomes and analyses not included in the multiplicity algorithm.

Date of last dose is collected on the *Treatment Discontinuation/Completion* eCRF page. For patients with missing or partial date of last dose, the date of last dose (ie, treatment end date) will be imputed. Date of last dose will be imputed as follows:

- Derive the number of tablets taken at the last visit as the dispensed amount minus the returned amount. For treatment compliance (Section 7.3) and exposure (Section 9.2), if the returned amount is missing, it will be assumed that zero tablets were taken. Otherwise, it will be assumed that 60 tables were taken.
- An estimated date of possible last dose will be calculated by adding the number of tablets taken divided by 2 to the visit date associated with the last visit where drug accountability was collected.
- If there is a partial date of last dose, missing day will be imputed using the day from treatment start date, or the last day of the month if that month has fewer days than the treatment start month.
- Treatment end date will be the minimum of the partial date of last dose, calculated estimated date of possible last dose, and collected study discontinuation/completion date.

Summary tables and data listings:

- Unless otherwise specified, no preliminary rounding will be performed; rounding will only occur after analysis.
- Data from patients excluded from an analysis population will be presented in the data listings but will not be included in the calculation of summary statistics, where applicable.
- Data from each patient will be separated by a blank line. Within a data listing, if a descriptive item appears line after line (e.g., repetition of a patient number, date, visit, etc.), only the first occurrence will be displayed (e.g., in Listing of Vital Signs, patient number, date and visit will only be displayed on first row when presenting all parameters collected at same visit). Repetition of actual results or outcomes (e.g., adverse events, lab results, vital sign values, etc.) will not be collapsed.
- Data listings will be sorted by treatment, patient, and date and/or time of assessment, as applicable.
- When change from baseline or change to baseline is calculated, baseline is the last observation obtained prior to first dosing of the study drug.
- Unless otherwise noted, values reported as greater than or less than some quantifiable limit (e.g., "< 2.0") will be summarized as using the numeric equivalent in summary tables and figures (e.g. "<2.0" will be analyzed as 2.0). The reported value will be used in listings.

Mock tables and data listings will be provided as attachments to this analysis plan. Minor changes to the mocks after formal SAP approval will not necessitate re-approval unless changes to the text of the SAP are required.

All statistical deliverables will be produced, validated, and reviewed for accuracy/consistency in accordance with standard operating procedures and the processes described in the statistical validation plan.

SAS® (SAS Institute, Cary, North Carolina) statistical software, version 9.4 or later, will be used for all analyses. Adverse Events and Medical History will be coded in Medical Dictionary for Regulatory Activities (MedDRA) Version 23.1. Concomitant medications will be coded in World Health Organization (WHO) Drug Version 2020-SEP and Anatomical-Therapeutic-Chemical (ATC) classification and preferred term.

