| Hospital Anxiety and Depression Scale (HADS)  |   | X                            |                               |                                  |    | X                        |                                    |
| Dispense study drug    |   | X                            |                               | X                                | X  |                          |                                    |
| Study drug accountability   |   |                              |                               | X                                | X  | X                        |                                    |
| Adverse events   | X   | X                            | X                             | X                                | X  | X                        | X                                  |
| Concomitant medications    | X   | X                            | X                             | X                                | X  | X                        | X                                  |

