## **9.3.** Treatment Compliance

At each scheduled study visit after randomization, the Investigator or designee will interview the patient regarding treatment compliance and compare the number of dispensed versus returned study drug tablets. Patients should strive for 100% compliance with the daily dosing schedule. Retraining on treatment compliance should occur for patients with less than 80% compliance, or greater than 100% compliance, at any visit and the Sponsor should be notified.

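### SAP 4 adds tablets already taken to the date of the visit that counted them, so an imputed last-dose date can be up to about 28 days late in some patients, and its missing-day rule has no link to the last dose

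*SAP*

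**What the plan says.** SAP 4 limits the rule to incomplete data: "For patients with missing or partial date of last dose, the date of last dose (ie, treatment end date) will be imputed". It has three parts.

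- **Tablet estimate.** "Derive the number of tablets taken at the last visit as the dispensed amount minus the returned amount". The estimated date is then obtained by "adding the number of tablets taken divided by 2 to the visit date associated with the last visit where drug accountability was collected". The sentence on missing return counts assumes zero tablets for compliance and exposure, and continues: "Otherwise, it will be assumed that 60 tables were taken".
- **Partial date.** The "missing day will be imputed using the day from treatment start date, or the last day of the month" if that month is shorter than the start month.
- **Minimum.** The treatment end date is the earliest of the filled-in partial date, the tablet estimate and the recorded study discontinuation or completion date.

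Protocol 9.3 has staff "compare the number of dispensed versus returned study drug tablets" at scheduled visits after randomization. In Protocol Table 2 and SAP Appendix 15.2, the row "Study drug accountability" is marked at Weeks 4 to 24 (or early termination) and not on Day 1. Dispensing is a separate row, marked from Day 1 to Week 20.

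**The concern.** A bottle dispensed at Week 8 and counted at Week 12 was used up between those visits. Adding its tablets, as days, to the Week 12 date runs the same four weeks again. The day rule has a different fault: the calendar day on which treatment began says nothing about the day on which it ended. Because the rule ends by taking a minimum, a filled-in date that is too early is never corrected.

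The treatment end date sets the denominator of derived compliance (SAP 7.3), days in study and days dosed (SAP 9.2), and the censoring time of non-responders in the Kaplan-Meier plot of time to SALT ≤20 (SAP 8.5). The cap at study exit gives little protection to patients who stop drug early, because Protocol 8.3 intends to follow them to Week 24, possibly months after their last dose.

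**Working it through.** The documents give no figure for this rule, so there is none to reproduce.

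**Inputs.** One 60-tablet bottle per 4-week visit (Protocol 9.4.2); 2 tablets a day (Protocol 9.4.3); visit windows of ±2 days (Protocol Table 2). Assumed: full adherence, visits 28 days apart, and start dates from 1 April to 31 December 2021, based on the planned study period. Error is the imputed date minus the true last-dose date.

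**1. Tablet estimate alone, bottle returned.** Let the bottle be dispensed on day D, counted on day C, and the last dose fall on day L. Tablets taken are 2(L - D).
- Anchor at the count: C + (L - D), so the error is C - D = 28 days. With ±2-day windows it is 24 to 32.
- Anchor at dispensing: D + (L - D) = L, so the error is 0.

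**2. Full rule, date fully missing, anchor at the count.**

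| Patient | Error (days) |
|---|---|
| Completes Week 24 and rolls over | 0 (capped at study completion) |
| Completes, does not roll over | +28 |
| Stops drug k days after start, study end at day 168 after start | min(28, 168 - k) |
| Leaves with an early-termination visit 7 or 14 days after last dose | at most +7 or +14 |
| Lost to follow-up, last bottle unreturned (study end assumed 60 days after last visit) | 0 to +30, with either anchor |

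For the third row, averaging over k = 1 to 167 gives (140 × 28 + 378)/167 = 25.7 days, where 378 is the sum of 1 to 27.

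**3. Effect on one patient's compliance.** A patient stops at the Week 12 visit (Day 85) after 168 tablets and stays in the study. The imputed date is Day 85 + 56/2 = Day 113. Derived compliance falls from 168/(2 × 85) = 98.8% to 168/(2 × 113) = 74.3%.

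**4. Partial date, completers.** The course is 168 days, about five and a half months, so the start day falls about half a month away from the end day.
- Start 1 June 2021: last dose 16 November, filled in as 1 November, error -15. Compliance is 336/(2 × 154) = 109%.
- Start 16 June 2021: last dose 1 December, filled in as 16 December, error +15.

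Over all the assumed start dates the filled-in day is off by -17 to +16 days, mean absolute 15.1. For non-rollovers that error stands, since the other two dates are both late. For rollovers the minimum removes the late half: 52% are exactly right, 48% are early, and the mean is -7.5 over all, or 7.5/0.48 = 15.6 days among those that are early.

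**5. Partial date, early stoppers.** With stop days spread evenly over days 1 to 167, the day rule alone is off by -30 to +30 days, mean absolute 10.2. Of these errors, 31% are 14 days or more and 38% are under 7.

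**6. Candidate remedies for a partial date, with the dispensing anchor.**
- Bottle returned, start-day rule kept: early stoppers are still off by -30 to 0 days, mean absolute 5.1. Moving the anchor does not cure this part.
- Bottle returned, tablet estimate used within the known month: 0 under full adherence.
- Bottle not returned, 60 tablets assumed: last day of the month gives a mean absolute error of 10.5 days, all of it late; the SAP's start-day rule gives 8.7.

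**The case against.** The strongest reply is that the anchor is ambiguous, not proven wrong. The case report form is not in the documents. If the accountability record carries the date of the visit that dispensed the bottle, the tablet estimate is exact under full adherence. The 60-tablet default suits a bottle handed out and never returned, and the SAP describes the result as a possible last-dose date, which reads like an upper bound. This reading is possible, but no document states it, and the schedule and Protocol 9.3 point the other way. Two programmers could differ by 28 days.

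The rest of the reply limits the size of the point, and it stands. A reader might infer any of the following, and the documents do not support them:
- **That imputed dates are generally wrong by two to four weeks.** The range is 0 to about 30 days in either direction; rollovers with a fully missing date have no error, and 69% of the day-rule errors in early stoppers are under two weeks. The two errors do not add, because the minimum selects one date.
- **That 74.3% crosses an operative 80% line.** Protocol 9.3 uses 80% for retraining at sites, and SAP 7.3 lists the case-report-form 80% category separately from derived compliance.
- **That both Kaplan-Meier plots are shown to be mis-censored.** SAP 6.1 describes censoring only for completers, at last treatment or 24 weeks. SAP 8.5 caps at 24 weeks and its p-values are descriptive.
- **That the Weeks 12 to 24 adverse-event denominator is wrong.** SAP 9.3 does not say that it uses the imputed date.

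Completers take a dose in clinic on visit days, so a partial date is least likely in the group where the day rule does worst.

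**Conclusion.** The point holds as a limited defect in a stated rule. Read with the schedule, the tablet estimate counts one dispensing interval twice for a returned bottle. With a fully missing date the end date is up to about 28 days late: +28 for completers who do not roll over, and 25.7 on average for patients who stop drug and stay to Week 24. With a partial date, the day is arbitrary and early errors survive the minimum.

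These sizes assume full adherence, 28-day visit spacing, start dates in April to December 2021 and an anchor at the counting visit. The number of patients with a missing or partial date is not given and may be small. Efficacy conclusions are not at risk: under Protocol 12.4.2 and SAP 8.2.1, SALT scores are used irrespective of treatment discontinuation, and neither the primary nor the key secondary analyses use the treatment end date. The case for acting is that derived compliance and exposure days would be wrong for identifiable patients, and the correction is cheap.

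**What to change.** In SAP 4:

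1. Anchor the tablet estimate at the date of the visit at which the counted, or unreturned, bottle was dispensed.
2. State when the 60-tablet default applies. Taken literally, the present sentence could override the actual count whenever a return is recorded.
3. When the month is known and the last bottle was returned and counted, use the corrected tablet estimate, limited to the known month, in place of the start-day rule.
4. When the bottle was not returned, no day rule is exact. Keep the existing rule or use mid-month. Last day of the month looks like the natural choice, but it is late by about 10 days on average and does worse here than the present rule.

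The cost is a few sentences and a small programming change, best made before database lock.
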